## **II. OBJECTIVE**

The goal of the study is to evaluate the efficacy of the light-emitting diode in the treatment of lower extremity surgical wounds left to heal by secondary intention by way of a double-blinded randomized, controlled study.

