## **III. STUDY PLAN**

Patients will be recruited from patients at the University of Miami Miller School of Medicine Mohs/Laser Unit. On the day of surgery and wound defect creation (day 0), patients will be informed of the study, and given the option of participating. If he or she decides to participate, the patient will be randomized into one of two groups in blocks of two by coin flip. The patient will remain blinded to the outcome of randomization. The experimental group will receive treatment with the light emitting diode (LED) for one session lasting 20 minutes of exposure at an intensity of 105 mW/cm^2 for a total of 126 J/cm^2 over the wound site. The LED emits light at wavelengths of 633 nm and 830 nm at fluences of 126 and 66 J/cm^2. This study will only utilize the 633 nm wavelength. The control group will receive sham light treatment for 20 minutes with standard of care for second intention healing and no LED treatment. In this case, a sham light treatment refers to regular light (not LED) exposure for 20 minutes. The sham light comes from the same device as the treatment light (Omnilux machine) however, this light has no anticipated effects on wound healing and is used simply to reduce the amount of bias that sometimes complicates the results of these studies. There is no added risk or benefit for the patients in the control group exposed to the sham light.

On day 0 the patients will be informed of the study and randomized into one of two groups by coin flip to either the experimental or control group. The patients will be blinded to which group they have been randomized too. Group 1 is the control group, which will receive sham light treatment and standard of care for lower extremity wounds. Group 2 represents the experimental group, which will receive LED treatment plus standard of care. The experimental group will receive treatment with the light emitting diode (LED) at 633 nm at one session lasting 20 minutes of exposure at an intensity of 105 mW/cm^2 for a total of 126 J/cm^2 over the wound defect, one week after wound creation (+/- 3 days). The control group will receive no LED treatment, however they will be exposed to a sham light for the duration of 20 minutes as well as receive standard of care for their lower extremity wound. Treatment will occur at one-week intervals (+/- 3 days) for a total

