of 4 treatments for both the experimental and control/sham groups. The wounds will be created as a result of Mohs micrographic surgery or surgical excision, and left to heal by secondary intention. An Aranz silhouette camera will be used with a measurement stick on the picture. Changes from the baseline wound (including length and width) will be measured along with wound depth. These two parameters will be compared at the 1 week, 2 week 3 week, and 4-week treatment (or sham treatment) visits. After the 4th and final treatment with the LED or sham light, the patients will be followed at 1-week intervals (+/- 3 days) until the wound has closed or for a maximum of 3 months, whichever occurs first. Once the wound has closed, patients will be evaluated a final time, 1 week after wound closure to ensure that complete wound healing has indeed occurred. After this final wound evaluation, the patient's commitment required for this study will end and regular follow-up with dermatology will resume outside the scope of this study.

The clinical photographs taken before and after either LED or sham light treatment at each study visit will be evaluated by blinded assessor(s) who are board-certified dermatologist(s).

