#### **IV. SUBJECT POPULATION**

##### **A. Number of Subjects**

We plan to prospectively enroll 40 patients in this study.

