## **VII. STATISTICAL CONSIDERATIONS**

This will depend on whether we want to measure a change between the experimental and control group at particular time intervals and between groups (ANCOVA) OR do we just want to measure the difference between the control and experimental groups at particular time periods (t test). If we just do a t test, then we will not be able to make intragroup comparisons, but it will be very easy to analyze, yet still determine if the experimental group accelerates wound healing in comparison to the control group. In addition, we should probably run an unpaired t test at baseline to make sure no statistically significant difference exists in wound

size between the experimental and control groups, otherwise it could confound our results one way or the other.

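### Two wound parameters are compared at four visits with the method undecided and no primary comparison, significance level or multiplicity rule, so a false significant difference is several times likelier than with one prespecified test.

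*Combined protocol and SAP*

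**What the plan says.** Section II gives only a general aim: "The goal of the study is to evaluate the efficacy of the light-emitting diode in the treatment of lower extremity surgical wounds". It names no outcome measure or time point.

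Section III (Study Plan) describes the measurements: "Changes from the baseline wound (including length and width) will be measured along with wound depth". It then sets the comparisons: "These two parameters will be compared at the 1 week, 2 week 3 week, and 4-week treatment (or sham treatment) visits". It also describes weekly follow-up after the fourth session until closure or for up to 3 months, a confirmation visit one week after closure, and blinded assessment of photographs. No analysis is assigned to any of these.

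Section VII (Statistical Considerations) is an open deliberation. It begins "This will depend on whether we want to measure a change between the experimental and control group at particular time intervals" and weighs ANCOVA against t tests at individual time periods without choosing. It mentions statistical significance only for a baseline check: "we should probably run an unpaired t test at baseline to make sure no statistically significant difference exists". It gives no significance level for efficacy.

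On size and allocation: "We plan to prospectively enroll 40 patients in this study", and patients are "randomized into one of two groups in blocks of two by coin flip".

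**The concern.** Two parameters at four visits give eight chances of a significant difference, and the plan does not say which one decides the trial. The method is open too, so it could be settled after the results are known. If any nominally significant result were then presented as evidence of efficacy, the false-positive rate would exceed that of a single test. A modest p-value at one visit would be hard to interpret, and an overall null result could be countered by pointing to another visit. The trial uses sham light and blinded assessors to limit bias, and an open choice of endpoint and method lets bias back in at the analysis stage.

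**Working it through.** **No figure to reproduce.** The documents state no significance level, power or overall error rate.

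**Inputs from the document.** Two parameters (size and depth) and four visits (Section III), so 2 × 4 = 8 comparisons. Forty patients (Section IV.A) in two groups in blocks of two (Section III).

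**Assumptions, not in the document.** Two-sided 0.05 per test, hence 0.025 in the direction favouring LED; 20 patients per arm; correlation 0.5 to 0.9 between adjacent visits, decaying with distance (AR(1)); correlation 0.3 to 0.7 between the two parameters; any significant result counts.

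**Step 1: independent tests.** Chance of at least one false significant result = 1 − (1 − α)^k.

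- Eight tests, either direction: 1 − 0.95^8 = 33.7%.
- Eight tests, favouring LED: 1 − 0.975^8 = 18.3%.
- Six tests, either direction: 1 − 0.95^6 = 26.5%.
- Six tests, favouring LED: 1 − 0.975^6 = 14.1%.
- Ceiling for eight tests under any correlation: 8 × 0.05 = 40%.

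**Step 2: correlated tests.** Trials with no treatment effect were simulated, using t tests on the values at each visit (20,000 trials per setting). Columns show visit correlation / parameter correlation.

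| | 0.5 / 0.3 | 0.9 / 0.7 |
|---|---|---|
| Eight tests, either direction | 29.9% | 17.2% |
| Eight tests, favouring LED | 15.3% | 8.4% |
| Six tests, either direction | 23.8% | 14.2% |
| Six tests, favouring LED | 12.0% | 7.1% |

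The six-test rows leave out week 1. Section III places the first light session one week after wound creation, so the week-1 comparison falls at that same visit. The plan does not say whether the wound is measured before or after the light. If before, week 1 cannot show an LED effect.

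**Step 3: the open method.** The same eight tests under each method, in a separate run of 6,000 trials per setting. Each cell gives either direction, then favouring LED.

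| | 0.5 / 0.3 | 0.9 / 0.7 |
|---|---|---|
| t test on visit values | 30.0%, 15.8% | 17.2%, 8.8% |
| t test on change from baseline | 25.4%, 13.4% | 21.9%, 10.8% |
| ANCOVA on baseline | 30.5%, 16.2% | 22.6%, 11.5% |
| t test on values or ANCOVA, whichever is significant | 36.1%, 19.4% | 32.3%, 16.6% |

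Over a wider grid (visit and parameter correlations each from 0 to 0.9), one fixed method gives about 13-34% in either direction and 6-19% favouring LED. Picking the better of two methods afterwards gives about 23-47% and 12-27%.

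**Step 4: after a fix.** One prespecified comparison has a 5% rate, of which 2.5% favours LED; the simulation gave 4.5-5.6%. Keeping all eight tests at 0.05/8 = 0.00625 gives 1 − 0.99375^8 = 4.9% if independent, and at most 5% under any correlation.

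**The case against.** The strongest reply is that the plan has no rule under which one significant result among eight means success. The inflation follows from what is left unsaid. If the ANCOVA option became one overall group test per parameter, there would be two tests and the either-direction rate would be at most 2 × 0.05 = 10%. That is correct, but the plan commits to no such test either, so the gap remains.

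Four stronger readings are tempting, and the documents do not support them:

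- A reader might take 17-30% as the chance of wrongly concluding that LED works. That range also counts results in which LED looks worse. The favourable half is about 8-15%, and its comparator is 2.5%, not 5%.
- A reader might count length, width and depth separately, making twelve tests. Section III speaks of two parameters, so eight is the plain reading, and only six would bear on efficacy if week 1 is measured before the light.
- A reader might treat 5% as the plan's own level. None is stated.
- A reader might conclude that no positive result could be distinguished from chance. A p-value below 0.00625 would survive Bonferroni correction over all eight tests. The difficulty is with modest p-values.

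It is also fair to say that the choice of primary outcome belongs to the sponsor. The defect is that none is named.

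**Conclusion.** The concern holds. The plan commits to repeated comparisons of two parameters, leaves the method open and has nothing to control the false-positive rate. For eight tests the chance of a false significant difference in either direction is about 17-30%, and about 8-15% for one that favours LED. The latter is roughly three to six times the 2.5% of a single test (8.4/2.5 = 3.4; 15.3/2.5 = 6.1). For six tests the figures are about 14-24% and 7-12%. Choosing the method afterwards raises them.

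The omission is plain from the text. The percentages are less certain: they rest on the assumed level, arm size and correlations, and on counting any significant result as a finding. Every setting tried with all the tests unadjusted gave a rate above that of a single test.

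**What to change.** Rewrite Section VII before any unblinded data are examined so that it names one primary comparison, with one method, at two-sided 5%. Either of these would serve:

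- **Wound size at one visit after LED exposure has begun**, by ANCOVA adjusted for baseline size. The visit could be week 4 or the first visit after the fourth session. State which size measure is used, whether it is taken before or after the light, and how a wound that has already closed is scored.
- **Time to confirmed closure.** Section I gives long healing time as the reason for the trial, and the weekly follow-up and confirmation visit are already planned. State what counts as closure, who judges it, which date is used given weekly visits with ±3-day windows, when the 3-month limit starts, and that wounds still open then are censored.

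Treat the other visits, depth and photograph ratings as secondary. Test them in a fixed sequence, adjust them (for example by Bonferroni or Holm), or report them descriptively with confidence intervals.

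**Cost.** No added visits or measurements. The sponsor gives up claiming success from any single visit. The wound-size option is mostly a matter of wording. Time to closure costs more: the closure and censoring rules must be written and some censoring accepted, since Section I says that healing often takes months. Whether 40 patients suffice should also be checked, because the document gives no basis for that number.

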The 830/633 nm LED has been used to improve wound healing after an Er:YAG/CO2 ablative laser system treatment. The experimental group received the 830/630 nm LED following ablative laser therapy while the control group received only the 630 nm LED after ablative laser treatment. The mean healing time for the experimental group was 6 weeks versus 13 weeks for the control group. Similarly, another study measured healing time after upper blepharoplasty and found healing time to be reduced one-half to one third in the 830/633 nm group. Another study using the LED (830/633 nm) treatment after Er:YAG laser ablation of deep plantar warts reduced the healing time by nearly half and reduced post-operative pain by 10% involving 121 subjects. Lower extremity ulcers have also been shown to be benefitted in terms of healing times by the 830 nm LED in a pilot study.

Wounds on the lower extremity heal more slowly than wounds on the head and neck and can remain deep red or violaceous for six months to one year. The decision to allow lower extremity wounds to heal by second intention is guided by a difficulty in using primary closure in many lower extremity wounds because of excess wound tension and limited tissue mobility. Decreased tissue laxity creates increased wound tension and an increased likelihood for wound dehiscence. By using second intention as a method for surgical defect management the physician

need not worry about dehiscence and retained suture material serving as a nidus for infection. Wound management is simple, requiring only a bandage and daily care that can be done at home by the patient, family, or visiting nurse. A major limitation of allowing surgical defects on the lower extremity to heal by second intention is the long healing time that can often take months. For this reason, modalities that can hasten this process are in demand.

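### Patients are followed weekly to confirmed wound closure, but no stated analysis uses closure or the time to it

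*Combined protocol and SAP*

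**What the plan says.** Section I gives the clinical problem as "the long healing time that can often take months". Section VII describes the simpler of its two candidate analyses as easy to run, "yet still determine if the experimental group accelerates wound healing in comparison to the control group".

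Section III sets the visits. Both arms have four weekly light sessions. Patients are then "followed at 1-week intervals (+/- 3 days) until the wound has closed or for a maximum of 3 months, whichever occurs first". For wounds that heal, the plan adds a confirmation step: "patients will be evaluated a final time, 1 week after wound closure to ensure that complete wound healing has indeed occurred".

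On what is compared, Section III refers to wound dimensions and depth: "These two parameters will be compared at the 1 week, 2 week 3 week, and 4-week treatment (or sham treatment) visits". It also has blinded dermatologists assess photographs taken before and after light treatment, but states no grade, closure judgement or comparison for them.

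Section VII leaves the method open. One option is to "measure a change between the experimental and control group at particular time intervals and between groups (ANCOVA"); the other is a t test between groups at particular times. It adds a baseline t test on wound size. No section names time to closure, proportion closed, censoring or a survival method. The list of recorded data in Section V has no closure date.

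**The concern.** The visit schedule is that of a time-to-event study: regular inspection until closure, a maximum duration and confirmation of the event. The analysis section does not use it. If the plan is followed as written, the weeks after the fourth session contribute to no comparison, and the most direct evidence on whether LED shortens healing goes unanalysed.

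There is a second, conditional risk. If the later data are analysed without a rule, two easy choices would mislead. Comparing wound size only among patients still attending keeps the slow healers. If LED works, more LED patients have left, so the comparison is tilted against it. Averaging healing time over closed wounds only discards the slowest healers, and more of them from the slower arm. The plan names neither analysis, but it does not exclude them.

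**Working it through.** **1. Visits set against analyses**

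- Day 0, wound size: baseline t test (Section VII).
- Weeks 1 to 4, dimensions and depth: comparison named in Section III, by t test or ANCOVA (Section VII).
- Weekly visits after the fourth session, to closure or 3 months: no analysis named.
- Visit one week after closure: no analysis named.

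**2. How much closure information lies after week 4**

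The documents give no closure rates for these wounds. As an illustration only, take the mean healing times of 6 and 13 weeks that Section I reports from a study of ablative laser treatment. That study concerned a different wound and compared 830/630 nm with 630 nm alone. Assume exponential healing times, 20 per arm ("We plan to prospectively enroll 40 patients in this study", "randomized into one of two groups in blocks of two by coin flip") and no dropout. The 3-month limit falls at about week 13 if counted from surgery, or about week 4 + 13 = 17 if counted from the fourth session.

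P(closed by t) = 1 − exp(−t/mean):

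- Week 4: control 0.265, LED 0.487; closures 20 × 0.752 = 15.0.
- Week 13: 0.632 and 0.885; closures 20 × 1.517 ≈ 30.4, of which about 15 come after week 4.
- Week 17: 0.730 and 0.941; closures 20 × 1.671 ≈ 33.4, of which about 18 come after week 4.

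Under either reading, about half of the closures fall after the last named comparison.

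**3. Size of the conditional bias, same illustration**

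The mean healing time among wounds closed by T is m − T·exp(−T/m)/(1 − exp(−T/m)).

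- T = 13: control 13 − 13 × 0.368/0.632 = 5.4 weeks; LED 6 − 13 × 0.115/0.885 = 4.3 weeks; difference 1.1.
- T = 17: control 13 − 17 × 0.270/0.730 = 6.7 weeks; LED 6 − 17 × 0.059/0.941 = 4.9 weeks; difference 1.8.

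A true difference of 13 − 6 = 7 weeks would appear as 1 to 2 weeks if open wounds were dropped.

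**4. What a time-to-closure analysis could detect**

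The plan gives no derivation of the 40 patients, so there is no figure of its own to reproduce. Assume two-sided alpha 0.05, 80% power, equal arms and proportional hazards. With E closures, the detectable rate ratio for an unadjusted log-rank test is exp(2 × (1.960 + 0.842)/√E) (Schoenfeld):

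- E = 40 (every wound closes): exp(5.603/6.325) = 2.43.
- E = 32: exp(5.603/5.657) = 2.69.

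A rate ratio of 2.0 needs 4 × 2.802²/(ln 2)² = 65.3, so 66 closures. With 32 to 40 closures its power is 50 to 59%. In the illustration of step 2, the rate ratio is 13/6 = 2.17 and power is 57% at the week-13 limit and 61% at week 17.

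**5. Sensitivity to the spread of healing times**

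Simulated log-rank power (1000 trials per setting, 20 per arm, weekly visits, control median 8, 10 or 13 weeks, limit at week 13 or 17), when LED halves the median:

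- Exponential times (rate ratio 2): 40 to 53%.
- Weibull shape 2 or 3 (rate ratio 2² = 4 or 2³ = 8): 97% or more.

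The spread decides the answer, and the documents do not give it.

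**The case against.** The strongest reply is that wound size over weeks 1 to 4 also measures speed of healing, that Section II's objective is only to evaluate efficacy, and that choosing time to closure is partly preference. This has force: it is why closure may be either the primary or a key prespecified endpoint. It does not explain why patients attend for up to three months and a confirmation visit with no analysis attached.

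Several stronger readings are tempting, and the documents do not support them:

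- A reader might infer that the planned comparisons are already biased by healed patients leaving. Exit after closure is described only for follow-up after the fourth session, beyond the week 1 to 4 visits at which comparisons are named. No section says closed wounds would be dropped.
- A reader might infer that a t test or ANCOVA cannot cope with wounds open at 3 months. For a size outcome it can, because an open wound has a measured size. The difficulty arises only when healing time is the outcome.
- A reader might infer that time to closure is far more powerful than a fixed-visit comparison. A t test at one visit with 20 per arm detects 2.802 × √(2/20) = 0.89 standard deviations. Without a spread for wound size or healing time, that cannot be ranked against a rate ratio of 2.4.
- A reader might take closure times as already recorded. They are only implied by the visit schedule, to within about a week.

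It is also fair to say that Section VII is undecided text, so this gap is one consequence of having no prespecified endpoint. It still has a specific remedy that uses visits already scheduled.

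**Conclusion.** The point holds as an omission in the analysis plan: closure is followed and confirmed but enters no stated analysis, while the question posed is whether LED accelerates healing. This rests on the text of Sections I, III, V and VII and on no simulation. It should be settled before any outcome data are examined.

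The figures are illustrative. That about half of closures fall after week 4, and that a 7-week difference would shrink to 1 to 2 weeks among closed wounds only, depends on exponential healing times borrowed from another type of wound. The bias arises only if such an analysis is done.

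Adding the endpoint does not make 40 patients adequate. At an assumed two-sided 5% level, 80% power for an unadjusted log-rank test needs a closure-rate ratio of about 2.4 even if every wound closes, and about 2.7 with 32 closures.

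**What to change.** Prespecify time to closure as the primary or a key endpoint:

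- **Origin.** Start the clock at randomization on day 0. The first light session comes about a week later and Section IV.B sets no minimum wound size, so a clock starting at first light could lose randomized patients whose wounds close before it.
- **Event.** Define closure, record its date as the first visit at which the wound is closed, and require confirmation at the existing one-week visit. State that a wound not confirmed closed remains under follow-up, and that the confirmation visit also applies to wounds first seen closed at the limit.
- **Limit.** State whether the 3 months run from surgery or from the fourth session. Censor wounds still open at that limit or at the last visit.
- **Analysis.** Show Kaplan-Meier curves by arm. Compare arms with a log-rank or Cox-type analysis adjusted for baseline wound area, using a method for grouped weekly times, which are tied and interval-censored (for example a discrete-time proportional hazards model). With 40 patients, take the p-value from a permutation test that respects the way patients were randomized.
- **Size analyses.** Count closed wounds as zero.

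The cost is plan wording, one recorded date and a little more analysis work. No visit is added beyond those Section III already describes. The plan should also acknowledge the modest power shown above.
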